3.3.3 Model validation and sensitivity

In all cases, standard statistical procedures will always be followed to ensure that no evidence indicates a violation of the assumptions underlying the statistical models used. Specifically, we note the following: secondary analyses based on the use of age as a continuous predictor in logistic regression models with treatment success as an outcome will be assessed using the Hosmer-Lemeshow goodness-of-fit test. Linear models will always be assessed using residual plots (residuals vs. predicted values, and QQ plots), together with tests for normality (Anderson-Darling and Shapiro-Wilk procedures). For mixed models, we will examine marginal residuals, conditional residuals, and EBLUPs.⁸ When modeling binary outcomes (using clustered logistic regressions), we will repeat analyses using a probit link as a check on robustness; we will also examine the Pearson goodness of fit statistic.⁹ Jackknife influence estimates will be used in all analyses; single observations that could change the conclusions will always be reported. Analyses in which time to response is used as the outcome variable (in which Cox regression is conducted) will be supplemented with the Gill-Schumacher procedure for assessing the adequacy of the proportional hazards assumption for Cox regression.¹⁰ Analyses in which our primary interest is in final outcomes will still be repeated using all available data (at all time points).

Failure of the modeling assumptions (such as normality) will result in conducting additional analyses. First, for continuous outcome variables, we will undertake normalizing or variance-stabilizing transformations of the outcome variable (such as power transformations). Second, robust procedures will be used to estimate the standard errors whenever possible. Third, the use of bootstrap procedures, when applicable, will be considered in estimation of standard errors.¹¹

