3.4 Sample Size Evaluation

3.4.1 Primary Calculation

The sample size for the trial will be 216 subjects, which we anticipate will provide approximately 80% power to detect a difference of 20% in the proportion of patients achieving control of inflammation at six months between the methotrexate and mycophenolate mofetil groups.

This sample size was determined based on the primary objective (superiority comparison of mycophenolate mofetil to methotrexate) and primary endpoint (treatment success). We assumed an effect size of 20%, as this was deemed to be clinically meaningful, and well within the distribution of the investigators' prior beliefs from published retrospective studies.

An approximate sample size is provided by the formula

$$2N = \frac{4(Z_{\alpha} + Z_{\beta})^2 \bar{p}(1-\bar{p})}{(p_c - p_i)^2} \quad (5)$$

(see Friedman et al. 2010), where α is the significance level (0.05, two sided), β is one minus the power (the desired power is 80%), p_c is in this case the probability of success in the methotrexate group (we estimate this at 0.4), p_i is the probability of success in the mycophenolate mofetil group (we estimate this at 0.6), and \bar{p} is $\frac{1}{2}(p_i+p_c)$. We assume 10% will be lost to follow-up in the first six months; details are given in the full proposal. This yields approximately 108 patients in each of the two groups, for a total of $2 \times 108 = 216$ subjects.

A power table is provided below as a sensitivity analysis (to show how the detectable effect size changes with varying success rates).

Success rate with Drug A	80% Power		90% Power	
	Detectable effect size	Success rate with Drug B	Detectable effect size	Success rate with Drug B
20%	18%	38%	21%	41%
30%	20%	50%	23%	53%
40%	20%	60%	23%	63%
50%	20%	70%	22%	72%
60%	19%	79%	21%	81%

Simulation confirms that this method yields adequate sample sizes for the logistic regression (results not shown).

Note that for the final analysis, the critical value will be adjusted slightly because of the interim analysis.

Sample size readjustment

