7.2 Adverse Events

7.2.1 Individual events

Adverse event reporting procedures are described fully in the MOP. Non-serious adverse events (not requiring narrative form) are described in the MOP (Section 6.1). Serious non-ocular or ocular adverse events (which must be reported within 24 hours and which require a narrative form) are described in the MOP (Section 6.2). Adverse events will be reported in all presentations and publications according to Consort guidelines.

The proportion of subjects with safety-related events will be compared using logistic regression, using treatment assignment and age as predictors, and including enrollment site as a random effect. Descriptive tables of the number and frequency of adverse events will be broken down by treatment arm, age, gender, and known comorbidities. We will report total adverse events and serious adverse events, cross-tabulated by whether the adverse events were anticipated or unanticipated and by whether or not the adverse event led to discontinuation of medication.

In addition, we will compare the rate of each of the adverse events during the follow-up period using Poisson regression, which can take into account multiple instances of adverse events within

a single subject. Age will be included as a predictor as well as treatment group, and enrollment site will be included as a random effect.

The additional statistical analysis of adverse events we describe here is undertaken strictly to provide additional insight which may be useful to the DSMC and investigators. Interpretation of such findings must reflect the fact that unanticipated adverse events may occur and that we may have insufficient power to make inferences between the arms when considering rare events. Note that adverse events contribute to the outcome of the trial and specific analyses have been defined earlier.

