7.2.2 Pooled adverse events

Adverse events will be analyzed according to four main categories:

- Proportion of subjects with *any ocular adverse event*
- Proportion of subjects with *any serious ocular adverse event*
- Proportion of subjects with *any systemic adverse event*
- Proportion of subjects with *any systemic serious adverse event*

The proportion of subjects with these events will be compared between the arms using Fisher's Exact Test. Poisson or negative binomial regression will be applied to compare the rates of overall adverse events, including recurrent events.

8 Reporting conventions

- All tables and data listings will be presented in landscape orientation, unless presented as part of the text of the final report.
- Figures will be presented in landscape orientation, unless the information is substantially easier to interpret in portrait orientation.
- Direct annotation of figures will be preferred to legends. All figures with more than one variable or item will contain either direct annotation or legends. All annotation will be unambiguously identifiable as such.
- Color will be used in figures only when needed to enhance clarity of communication. All color schemes will be evaluated for visual clarity for individuals with diminished color vision. All color encodings will be identified. Redundant encodings (such as the use of different plot symbols or line dash patterns) will be used in addition to color, so that all figures are interpretable after monochrome reproduction at 100 dots per inch. All dash patterns and line widths will be adequate to be distinguishable after monochrome reproduction at 100 dots per inch. Any distinction between plot symbols (circles, filled circles, diamonds, etc.) will remain clear after monochrome reproduction at 100 dots per inch.
- Fixed width sans serif fonts will be used for all labeling (Helvetica, Arial, or Futura).
- Boldface and italics will not be used unless substantial value is added.

- Decorative fonts and enhancements, including borders and shading, will not be used. Decorative presentation methods, such as ribbon graphs, will never be used.
- All information given in figures will also be presented in summary tables (perhaps only included in an Appendix or in supplementary materials).
- Only standard characters will be used in tables and data listings.

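### SAP 7.2.1 compares individual adverse event rates by plain Poisson regression, whose standard errors are too small if some patients are more event-prone than others

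*Combined protocol and SAP*

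**What the plan says.** SAP 7.2.1 plans a logistic comparison of the proportion of patients with safety-related events. It then adds a comparison of the rate of each adverse event "during the follow-up period using Poisson regression, which can take into account multiple instances of adverse events within" one subject. On the terms of the rate model it says: "Age will be included as a predictor as well as treatment group, and enrollment site will be included as a random effect". It names no patient-level effect, dispersion parameter or robust variance. The same section describes the modelling as "undertaken strictly to provide additional insight which may be useful to the DSMC and investigators".

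SAP 7.2.2 compares the proportions with any ocular or systemic event, serious or not, by Fisher's exact test. For counts it says: "Poisson or negative binomial regression will be applied to compare the rates of overall adverse events, including recurrent events". It gives no rule for choosing between the two models.

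SAP 3.3.3 promises that "standard statistical procedures will always be followed to ensure that no evidence indicates a violation of the assumptions underlying the statistical models used". If modelling assumptions fail, "robust procedures will be used to estimate the standard errors whenever possible". It lists specific checks for logistic, linear, mixed, clustered binary and Cox models, and none for count models.

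The rate of adverse events is a listed secondary outcome (protocol 2.1; SAP 2.3.1).

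**The concern.** The reason given for Poisson regression covers only half of what repeat events require. The model accepts counts above one. It also sets the variance of a patient's count equal to its mean, which amounts to assuming that patients with the same covariates all share one underlying rate. If some patients are prone to repeated nausea or fatigue and others have none, counts vary more than that. The treatment standard error is then too small, and confidence intervals are too narrow.

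The site random effect does not help, because it absorbs differences between sites and not between patients within a site. Heterogeneity is plausible here. Protocol 6.1 gives gastrointestinal upset, nausea, vomiting and fatigue as examples of events, and protocol 6.3 records events at every study visit. SAP 3.4.2 expects 13% of methotrexate patients and 4% of mycophenolate patients to stop for tolerability, so it already expects patients to differ in how they tolerate treatment.

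What is at stake is how the safety rates are read. SAP 6.2.3 leaves stopping for harm to the DSMC's judgement without fixed boundaries, and this modelling is meant to inform that committee.

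**Working it through.** **Sample size.** The plan states: "The sample size for the trial will be 216 subjects". SAP Equation (5) with success rates 0.4 and 0.6, two-sided 0.05 and 80% power gives 2N = 4 × (1.960 + 0.842)² × 0.25 / 0.04 = 196.2, and 196.2 / 0.9 = 218.0, close to 216. A standard two-proportion calculation gives 97 per arm, and 97 / 0.9 = 107.8, rounded up to 108, matches the plan. This figure serves only as the n per arm below.

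**Assumptions.** The documents give no adverse event rate, dispersion or alpha for this comparison. I therefore vary the mean count per patient (m) and the between-patient gamma variance (k), and take a two-sided 5% test.

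**Formula.** If patient rates vary as a gamma variable with mean 1 and variance k, a count has mean m and variance m(1 + km). With n per arm and no drug difference:

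- Poisson standard error of the log rate ratio: √(2 / nm)
- true standard error: √(2(1 + km) / nm)
- ratio: √(1 + km), in which n cancels
- real error of the nominal 5% test: 2[1 − Φ(1.96 / √(1 + km))]

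Example with n = 108, m = 1, k = 1. The Poisson standard error is √(2/108) = 0.136 and the true one is √(4/108) = 0.192, a ratio of 1.41. Then 1.96 / 1.41 = 1.39, and the real error is 16.6%.

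**Results.** Real error of plain Poisson at nominal 5%, by formula. Brackets give a simulation with 108 per arm, nine sites, and treatment, age and site in the model (2,000 runs per cell; site fitted as fixed intercepts in place of the random effect).

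| Mean count | k = 0 | k = 0.5 | k = 1 | k = 2 |
|---|---|---|---|---|
| 0.1 | 5.0% | 5.6% | 6.2% | 7.4% |
| 0.25 | 5.0% | 6.5% | 8.0% | 11.0% |
| 0.3 | 5.0% [4.3%] | 6.8% [7.1%] | 8.6% [8.8%] | 12.1% [12.6%] |
| 0.5 | 5.0% | 8.0% | 11.0% | 16.6% |
| 1 | 5.0% [4.9%] | 11.0% [10.9%] | 16.6% [18.0%] | 25.8% [26.0%] |
| 2 | 5.0% [5.2%] | 16.6% [17.7%] | 25.8% [25.6%] | 38.1% [38.6%] |

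The site term was in every simulated model and did not remove the inflation.

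**Alternatives.** In the same simulation, robust standard errors gave 4.6% to 7.0% across the cells, and scaling by the Pearson dispersion gave 4.3% to 7.4%. In a separate simulation (600 runs per cell, treatment and age only), negative binomial regression gave 4.2% to 6.3%. Those figures use only fits that returned a usable standard error. With k = 0, that was 434 to 481 of 600 runs; with k = 1 or 2 it was nearly all (590 to 600).

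**The case against.** The case for leaving the text alone has five parts.

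1. **SAP 3.3.3 already promises assumption checks and robust standard errors.** This is a real safeguard and offers one of the remedies proposed here. But it acts only after a failure is found, it names no check for count models, and it does not specify patient-level clustering. The reason stated in 7.2.1 tells the analyst that repeat events are already handled, so nothing there prompts a check.
2. **SAP 7.2.2 allows negative binomial regression for overall recurrent events.** True. A reader might infer that every recurrent-event comparison is tied to Poisson, and the documents do not support that. What remains is the event-by-event model in 7.2.1 and the missing selection rule in 7.2.2, which leaves the choice open until the data are seen.
3. **The analysis is supplementary.** This stands. A reader might infer that the trial's tolerability finding or its main result is at risk. The planned tolerability comparison is discontinuation by reason (SAP 3.2.2, item 6), and intolerance enters the primary outcome as a binary failure. Repeat events affect neither, nor the logistic and Fisher tests on proportions. The plan also sets no alpha for the Poisson comparison, so the error rates above describe a conventional 5% reading.
4. **The inflation may be small.** It may. Each event is modelled separately, so means may be low. The adverse event log records onset and resolution, so persistent nausea may count once. A reader might infer that Poisson regression cannot use repeat events or always fails. It does use them, and it is valid when counts are not overdispersed.
5. **A rate during follow-up already implies a time denominator.** Largely so; the missing offset is mainly a missing detail. It is still worth stating, because time on the first drug depends on success. With success rates of 0.4 and 0.6, twelve months for successes and a full six for failures, the means are 0.4 × 12 + 0.6 × 6 = 8.4 months and 0.6 × 12 + 0.4 × 6 = 9.6 months.

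**Conclusion.** The point holds in a limited, conditional form. For individual adverse events, SAP 7.2.1 names only a model that ignores differences in event-proneness between patients, and justifies it by a property that does not address them. The size depends on the product of mean count and between-patient variance, and the documents give neither. For rare events the effect is minor. For events averaging one per patient, with variance between 0.5 and 2, true standard errors are 1.22 to 1.73 times those reported, and the real error is 11% to 26%. Because the direction is known and the alternatives restore the error to near 5%, the change should be made, although it bears on a supplementary analysis of a secondary outcome and not on the primary conclusion.

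**What to change.** In SAP 7.2.1 and 7.2.2, prespecify negative binomial regression with log follow-up time as offset, keeping treatment, age and site as in 7.2.1. Poisson regression with patient-level robust standard errors and the same offset is an acceptable alternative. Choose one now, so that 7.2.2 no longer offers two models without a rule. If negative binomial is chosen, name the robust Poisson model as the fallback when the fit fails, which the simulation suggests is most likely when there is little overdispersion. Replace the stated reason with one that says repeat events are counted and that between-patient variation is allowed for in the variance. Leave the proportion-with-event analyses as they are.

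The cost is a few sentences in the SAP and no new data. Intervals widen where counts are overdispersed, by about 40% on the log scale at mean 1 and variance 1 (√2 = 1.41). That is the correct width under those assumptions.

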7.2.2 Pooled adverse events

Adverse events will be analyzed according to four main categories:

- Proportion of subjects with *any ocular adverse event*
- Proportion of subjects with *any serious ocular adverse event*
- Proportion of subjects with *any systemic adverse event*
- Proportion of subjects with *any systemic serious adverse event*

The proportion of subjects with these events will be compared between the arms using Fisher's Exact Test. Poisson or negative binomial regression will be applied to compare the rates of overall adverse events, including recurrent events.

8 Reporting conventions

- All tables and data listings will be presented in landscape orientation, unless presented as part of the text of the final report.
- Figures will be presented in landscape orientation, unless the information is substantially easier to interpret in portrait orientation.
- Direct annotation of figures will be preferred to legends. All figures with more than one variable or item will contain either direct annotation or legends. All annotation will be unambiguously identifiable as such.
- Color will be used in figures only when needed to enhance clarity of communication. All color schemes will be evaluated for visual clarity for individuals with diminished color vision. All color encodings will be identified. Redundant encodings (such as the use of different plot symbols or line dash patterns) will be used in addition to color, so that all figures are interpretable after monochrome reproduction at 100 dots per inch. All dash patterns and line widths will be adequate to be distinguishable after monochrome reproduction at 100 dots per inch. Any distinction between plot symbols (circles, filled circles, diamonds, etc.) will remain clear after monochrome reproduction at 100 dots per inch.
- Fixed width sans serif fonts will be used for all labeling (Helvetica, Arial, or Futura).
- Boldface and italics will not be used unless substantial value is added.

- Decorative fonts and enhancements, including borders and shading, will not be used. Decorative presentation methods, such as ribbon graphs, will never be used.
- All information given in figures will also be presented in summary tables (perhaps only included in an Appendix or in supplementary materials).
- Only standard characters will be used in tables and data listings.
- All titles will be centered. The first title line will be the number of the table, figure, or listing. The second and possibly third lines will be the description of the table, figure, or data listing. The ICH numbering convention will be used for all.
- All footnotes will be left justified and at the page bottom. Footnotes will be used sparingly. Reference footnotes will be complete enough to locate any reference based on the information provided (Author, Journal, Pages, Date, or PubMed accession number).
- Missing values for numeric or character variables will be unambiguously identified as such using the special string **NA** (not available) in all settings; **NA** is the standard missing value code for our software. Each figure or table caption in which **NA** is used will indicate the meaning of **NA** in that figure or table. The abbreviation **NA** will never be used for any other purpose.
- All date values will be presented in the form DDmmmYYYY format (e.g. 01jan2008), using four digit years. June will be encoded as **jne** (otherwise **jan** and **jun** would differ by only a single character), and July as **jly** (so that the lowercase letter **l**, easily confused with the digit **1**, will not be adjacent to any numerals).
- All tables, figures, and data listings will have the name of the program and a date/time stamp on the bottom of the output.

9 Abbreviations and acronyms

AES Advanced Encryption Standard

CAS Chemical Abstracts Service

DSMC Data and Safety Monitoring Committee

FAST First-line Antimetabolites as Steroid-sparing Treatment

FIPS Federal Information Processing Standard

ICH International Conference on Harmonization

logMAR log of minimum angle of resolution

MOP Manual of Operations and Procedures

[REDACTED]

NIST National Institute of Standards and Technology

SAP Statistical Analysis Plan

[REDACTED]

[REDACTED]

[REDACTED]

[REDACTED]

[REDACTED]

[REDACTED]

10 Appendix

All computations will be performed using the standard software package R (<http://www.r-project.org>). Statistician [REDACTED] has twenty years of experience using R or very similar statistical computing environments (S, S-Plus).

Specification of the random number seed and pseudorandom number algorithm determines the entire randomization assignment (as is the case with any pseudorandom number generation method). Accordingly, the random number seed will be kept confidential, and the seed will be chosen carefully. In particular, easy-to-remember numbers or otherwise meaningful numbers (such as telephone numbers, birthdays, and so forth) are to be scrupulously avoided. The chosen seed will be used to generate the final randomization lists.

A printed copy of the randomization lists for all sites, the computer code used to generate them, and the random number seed will be maintained in a locked vault off site. The random number seed chosen will consist of at least eight digits, and a standard linear feedback shift-register algorithm will be used for pseudorandom number generation.²⁹

11 Document Revision History

13 January 2015

2.3.1 Specific Aim 1

- Added secondary analysis: To evaluate a difference in treatment success controlling for vasculitis at baseline, assessed at six months.
- Added secondary analysis: To explore the use of a dynamic process model (such as a Hidden Markov model) to assess differences in control of inflammation.

2.4.1 Stratification between sites

- Updated: Patients will be recruited from nine sites: [REDACTED]

[REDACTED] (see Manual of Operations Section 2.2 for details).

2.4.4 Unique patient identifiers

- Updated for correct number of sites: Unique patient identifiers will be generated as follows. The first character will be a number: [REDACTED]

3.2.2 Planned Analysis of Primary Outcome

- Added non-inferiority analysis with a prespecified non-inferiority limit if the primary outcome is no statistically significant.

3.5.1 Injections (New Section)

- Added section: If a patient receives a corticosteroid injection 90 days after enrollment, it is not possible to truly assess the study drug's ability to manage inflammation at the Month 6 visit. Therefore, as a sensitivity analysis, the primary outcome for these patients will be considered by the inflammation levels at the time of the injection. If the patient received the injection because of uncontrolled inflammation, the patient will be considered a treatment failure. If the patient met the definition of treatment success at the time of the injection, the patient will be considered a treatment success.

